## 8.2 Process and responsibilities for reporting SAEs

All SAEs will be recorded on the relevant form of the CRF (see appendix) and reported to the PI and chair of the DMEC within 48 hours of receiving the report. The Programme Manager or Trial Manager is responsible for reporting to the PI and Chair of DMEC.

The PI and chair of the DMEC will consider whether the SAE is: not related to participation, possibly related to participation or definitely related to participation. Judgement will be made on whether to report the possibly related cases on to the Sponsor and ethics committee chair, but all cases of definitely related will be reported onwards.

A cumulative review of all safety information by the TSC/DMEC will be made on 6 monthly basis.

All SAEs will be followed up where appropriate by the researcher, the intervention coordinator or the women's worker. If it is felt that a child or adult are at significant risk, then the standard safeguarding procedure will be initiated, as outlined in the Safeguarding Flowchart, appendix 2.

All adverse event reporting will be in accordance with the UH Bristol 'Research Safety Reporting Policy'

(http://www.uhbristol.nhs.uk/media/2518477/research\_safety\_reporting\_sop\_009\_uhbri stol\_r\_i\_v8.0\_19.10.15.pdf.

The statistician will remain blinded to group allocation relating to AE/SAE reporting.

## 8.3 Data Monitoring and Ethics Committee (DMEC):

In accordance with the Trial Terms of Reference for the DMEC, periodically reviewing overall safety data to determine patterns and trends of events, or to identify safety issues, which would not be apparent on an individual case basis will be undertaken.

#### 8.4 Programme Steering Committee (PSC):

In accordance with the Trial Terms of Reference, the DMEC will report its periodic review of safety data to the PSC.

#### 8.5 Notification of deaths

All deaths will be reported to the sponsor irrespective of whether the death is related to participation in the trial. This information will be passed to the sponsor within 24 hours of receiving the notification by the Programme Manager in lieu of a trial manager.

## 9 STATISTICS AND DATA ANALYSIS

For the purposes of this pilot trial, data will be analysed and reported using descriptive statistics only as the pilot is not sufficiently powered for a comparison of outcomes between the groups. However, the findings from this pilot will inform the power calculation required for the full trial and a Statistical Analysis Plan will be produced once the findings from this pilot are reviewed and it is clear that progression to a full trial will happen. The SAP will be developed once the full trial primary and secondary outcomes are determined. Data on recruitment, randomisation and retention will be collected and recorded in line with CONSORT guidelines. All secondary outcome measures will be analysed and presented by trial arm for the baseline and 9 month time point to inform trial primary objectives.

#### 9.1 Analysis of nested qualitative study

Interviews with participants will be audio-recorded and transcribed for analysis professionally. The audio aspect of the video data will be transcribed professionally (depending on budget availability) and supplemented with observational data by the researchers. For any informal observations about context for example, the researcher will summarise and write up their more detailed field notes for sharing. The interview and observation transcripts will be individually read and re-read, from which an initial coding framework will be developed. This framework will be added to and refined, with coded material regrouped as new data from subsequent interviews / video data is gathered. We will analyse the data sets thematically. We will triangulate the different data sources. Data analysis for the interviews and observational data will be broadly thematic. NVivo will aid data management, and enable comparisons/build relationships between the different parts of the data (e.g. interview data with perpetrators, partners /ex partners and providers, observation data and field notes). The codes will gradually be built into broader categories and themes. The data will be scrutinised for differences and similarities within themes across groups/interviewees, seeking disconfirming as well as confirming cases. One researcher will lead the analysis of each sub dataset e.g. of perpetrators or providers, but other team members will independently code a sub-sample of transcripts for inter-rater reliability. All team members will meet to discuss the preliminary coding framework and themes and to ensure that the emerging analysis is trustworthy and credible. An extract of the coding framework may also be considered at the PPI groups for discussion.

#### 10 DATA HANDLING

#### 10.1 Data collection tools and source document identification

#### Source Data and documents

Source data for this trial will be the confidential data collected by the DVPP coordinator during the risk assessment procedure for men and the women's worker needs assessment for the women. These documents will remain the property of the service provider, but will be made available to the research team to verify contact information given to the researcher. To this end, the source documents will be the information recorded by the service providers in their confidential files.

Since the research team will need to collect information on number of contacts made, then access to source data will be agreed at the outset of the trial.

## **Case report forms**

A case report form (CRF) will be prepared for each participant to record all data required by the trial protocol. It will be a printed document, the contents of which will be entered onto the database for statistical analysis.

## 10.2 Data handling and record keeping

Administrative data including names, addresses and other personalised data will be stored in the University of Bristol (UOB) SQL Server Cluster and entered using an MS-Access frontend. We will not be using MS-Access to store data.

Clinical data are collected using the BRTC Redcap software. REDCap is a secure, web-based electronic data capture (EDC) system designed for the collection and management of research (as distinct from administrative) data. Although the REDCap system has been developed (and it is supported) by Vanderbilt University, SSCM has set up its own infrastructure to host the REDCap application so that all elements reside within UoB.

All clinical data is stored in a secured UoB server subject to standard UoB security procedures. The full database is backed up daily and any changes to the database are logged every 5 minutes. A disaster/recovery plan is in place so that the data could be restored to the latest 5 minute backup.

A combination of field type validation, data ranges, logic and thorough testing is used to ensure the quality of the data collected via REDCap. Clinical data are anonymised by Identification Code and all data collection are made by Identification Code.

REDCap user roles can be used in combination with filed validation as identifier to determine the data that can be viewed by different members of the team. This facility can be used to avoid unblinding the statistician if necessary.

Clinical data entry can be performed by accessing the REDCap application directly or via surveys. In order to access the application directly, users from the research team will be added to the system (following request from the Programme Manager) by the Data Manager. It is the Programme Manager's responsibility to add the user to a specific project and role.

Both Clinical and Administrative data are secured using robust security mechanisms. Both systems also have audit logs cataloguing individual changes with data/time, old value, new value and the identity of the user who made the change.

Both systems are managed by UOB Information Services and have backup facilities including dumps to tape and snapshots. Any data transfer is done either using UOB systems secured by the University's Active Directory system linked to each user's identity. Files transferred external to UOB will use encrypted files over the UOB secure file transfer facility (FLUFF).

## 10.3 Access to Data

Data can only be accessed by authorised accounts and authorisation can only be granted by specific people such as the CI, the Programme Manager, or the research team.
## 10.4 Archiving

- archiving will be authorised by the Sponsor following submission of the end of study report
- the questionnaire data will be archived
  - the location and duration of record retention for essential documents and the trial database will be recorded.
- all essential documents will be archived for a minimum of 5 years after completion of trial
- destruction of essential documents will require authorisation from the Sponsor

## 11 MONITORING, AUDIT & INSPECTION

- A Trial Monitoring Plan will be developed and agreed by the Trial Management Group (TMG) and TSC based on the trial risk assessment which may include on site monitoring.
- The University of Bristol has a Service Level Agreement with UHBristol whereby the NHS Trust monitors 10% of the University's Sponsored studies.

## 12 ETHICAL AND REGULATORY CONSIDERATIONS

## 12.1 Research Ethics Committee (REC) review & reports

- before the start of the trial, approval will be sought from a REC for the trial protocol, informed consent forms and other relevant documents e.g. advertisements
- substantial amendments that require review by REC will not be implemented until the REC grants a favourable opinion for the study
- all correspondence with the REC will be retained in the Trial Master File/Investigator Site File
- an annual progress report (APR) will be submitted to the REC within 30 days of the anniversary date on which the favourable opinion was given, and annually until the trial is declared ended
- it is the Chief Investigator's responsibility to produce the annual reports as required.
- the Chief Investigator will notify the REC of the end of the study
- if the study is ended prematurely, the Chief Investigator will notify the REC, including the reasons for the premature termination
- within one year after the end of the study, the Chief Investigator will submit a final report with the results, including any publications/abstracts, to the REC

## 12.2 Peer review

An outline of this pilot trial was included in the NIHR grant application that was approved for funding. This was extensively peer reviewed (10 independent reviewers and the PGfAR panel). This protocol was reviewed by members of the TSC prior to submission for Sponsor approval and REC submission.

Protocol version 2.0 09/02/2018\_track changes

## 12.3 Public and Patient Involvement (PPI)

We have active PPI groups informing our research. A group of female survivors (women who have experienced DVA) and a separate group of male ex-perpetrators (men who have been through a DVPP) have informed the design of the research and the intervention. Both groups have input into the recruitment material including the PIS and ICF process. Regular planned meetings will help inform issues around recruitment and retention of participants.

Our PPI groups will also be involved in the planning of the qualitative interview questions, the interpretation of the findings and either the planning for the full trial, or the dissemination of the pilot findings.

## 12.4 Protocol compliance

All changes to this protocol that may be required as part of the pilot trial will be documented and submitted for approval. No participant will knowingly be enrolled as a trial participant if they do not meet the eligibility criteria or restrictions specified in the trial protocol.

Any accidental deviations from the protocol will be adequately documented on the relevant forms and reported to the Chief Investigator.

## 12.5 Data protection and patient confidentiality

All investigators and trial site staff must comply with the requirements of the Data Protection Act 1998 with regards to the collection, storage, processing and disclosure of personal information and will uphold the Act's core principles.

Personal information on research participants will be collected and kept secure by the creation of a coded, depersonalised database where the participant's identifying information is replaced by an unrelated sequence of characters. This will be securely maintained with the linking code in separate locations using encrypted digital files within password protected folders and storage media. Access to this data will be limited to the research team with responsibility for data entry and analysis.

Anonymised data will be made public via a data sharing initiative. Personal details will be kept for 5 years after participation. The custodian of this will be the CI at the University of Bristol.

# 12.6 Financial and other competing interests for the chief investigator, PIs at each site and committee members for the overall trial management

The development of the domestic violence perpetrator programme involves a number of partners who are collaborators in this research. A memorandum of understanding will be prepared by the University of Bristol Research Commercialisation Manager intellectual property will be a standing item on the trial steering group.

## 12.7 Indemnity

This study will be sponsored by the University of Bristol. The University has Public Liability insurance to cover the liability of the University to research participants.

## 12.8 Amendments

All updates to this protocol and approvals thereof will be conducted and recorded in the appropriate way.

Protocol version 2.0 09/02/2018\_track changes

- amendments will be made once the decision at the TSC/DMEC or other programme advisory group has been documented.
- The programme manager or trial manager will decide whether the amendment is substantial or non-substantial
- substantive changes will be communicated to relevant stakeholders (e.g., REC, trial registries, R&D, regulatory agencies in accordance with the latest advice and guidance.
- the amendment history will be tracked to identify the most recent protocol version and this will be available as an appendix to this protocol and within the Trial Master File.
- Guidance on the categorisation of amendments can be found on the HRA website. http://www.hra.nhs.uk/resources/after-you-apply/amendments/

## 12.9 Post trial care

Participation in the DVPP intervention will be for approximately 26 weeks. Evidence suggests that following this, some men benefit from an informal follow-on group, which may need to be funded separately. The trial follows participants up for 3, 6 and 9 months post-randomisation. It is likely that after this time we would sign-post men and women to relevant ongoing support agencies if this were necessary.

## 12.10 Access to the final trial dataset

• The statistician, database manager and research fellows will have access to the full dataset but a master copy will be protected.

## 13 DISSEMINATION POLICY

For academic publications we will follow the Consort Guidelines and checklist prior to generating any publications for the trial to ensure they meet the standards required for submission to high quality peer reviewed journals etc. http://www.consort-statement.org/

- The University of Bristol owns the data arising from the trial
- On completion of the pilot trial, the data will be analysed and tabulated and a Final Study Report prepared. This will feed into the main trial protocol which will follow this pilot if the intervention and trial methods are acceptable.
- Any dissemination of this pilot trial (either academic or lay) will be done in discussion and agreement with the participating investigators
- The NIHR require that they have one month to review publications prior to submission.
- The NIHR require that funding needs to be acknowledged within all publications: Disclaimer/acknowledgement thus:

"This report is independent research funded by the National Institute for Health Research (Programme Grants for Applied Research, REPROVIDE (Reaching Everyone Programme of Research On Violence in diverse Domestic Environments), RP-PG-0614-20012). The views expressed in this publication are those of the author(s) and not necessarily those of the NHS, the National Institute for Health Research or the Department of Health."

- We will prepare and publish a quarterly newsletter that will be made available via our website. The audience for this will be aimed at our PPI group members, but trial participants will also be encouraged to access this if they want to know the outcome of the trial. For participants or PPI members who cannot access the internet, a paper copy in the post will be made available if it is safe to send to the given address.
- For the pilot trial we will not publish the protocol, but if a favourable outcome means that the full trial goes ahead, we would publish the trial protocol. The full study report, anonymised participant level dataset, and statistical code for generating the results will be made publicly available following the completion of the trial and programme, estimated to be in 2022/23.

## 13.1 Authorship eligibility guidelines and any intended use of professional writers

- The main author of the final report will be first author and all other contributors will be listed in alphabetical order. The last author will be the CI.
- All publications that arise from this trial will use the criteria for individually named authors or group authorship (The International Committee of Medical Journal Editors has defined authorship criteria for manuscripts submitted for publication) and this will be agreed in advance.

## **Required documentation**

## **REPROVIDE RCT Pilot Perpetrator Programme**

## **Pilot Trial Master File Contents**

Section	Details	Who	Completed by	Version number	Date & version of update	Comments
1	Protocol:					
2	Patient Information: 
 
Participant information sheet - trial
 
Men
 
Women
 
Participant information sheet interviews
 
Men
 
Women
 
Professionals
 
Participant information sheet
 
	Men	КМ	V5.	18.07.2017	
	
 
information sheet – subgroup interviews
 
all
 
Informed Consent form (ICF)
 
Men x 2
 
Women x 2
 
Professionals x 1
 
Subgroup interviews x 1
 
Recruitment Strategy
 
Advertisements for participants
 
Recruitment flyer for men
 
	Men Men	км	V5 1.1	18.07.2017 11.07.2017	
3	Approvals / Regulatory: - REC approval - ISRCTN registration - Other applicable approvals -					
4	Agreements/ funding: - Copy of any signed agreements between involved parties					

	
 
Sponsorship agreements / sponsorship letter,
 
Copy of financial information (funding application/ award letter/ R&D costings)
 
Insurance/ Indemnity certificates or statements
 
Petty cash
 

5	Research Team – Staff and
	training
	
 
Signed and dated CV of Investigators and research team as appropriate
 
Delegation log
 
Evidence of GCP training (if not stated in CV)
 

6	Consent forms:
0	- Signed participant consent forms
7	Data collection:
	
 
Trial case record forms (CRFs)
 
Agreement with BRTC
 
Database instructions
 
Statistical analysis plan
 

8	Safety:
	
 
Adverse Event reporting
 
Serious Adverse Event forms
 
Reporting pathway
 

9	Reports:
	
 
Annual progress reports
 
Final Study Report (after completion of trial)
 

10	General correspondence
	
 
Trial Management Group (TMG)
 
Data Monitoring Ethics Committee (DMEC)
 

Protocol version 2.0 09/02/2018\_track changes

	
 
REPROVIDE Advisory Group (PAG)
 
Miscellaneous correspondence
 
-
 
		
11.	StandardOperatingProceduresSafety and Ethical considerations-Data entry		

# 15.4 Appendix 4 – Schedule of Procedures

Procedures	
Informed consent	1
Eligibility assessment	1
Risk assessment	1
Randomisation: Intervention attend DVPP – men; support for women Control men (questionnaires only) Control women, support signposted	Up to 26 weekly visits of a DVPP. Reminder phone calls when questionnaire is being sent out.
Baseline questionnaires	In person
3 month questionnaires	Post or in person
6 month questionnaires	Post or in person
9 month questionnaires	Post or in person

## 15.5 Appendix 5 – Safety Reporting Flow Chart

#### SERIOUS ADVERSE EVENTS (SAE)

All SAEs should be reported and the relevant form completed by the researcher/facilitator. This should be sent to the Programme Manager who will notify the CI ([name]) and Chair of DMEC within 48 hours.

The CI DMEC Chair will decide whether the SAE is:

- 1. Definitely related to intervention/participation? This will require a report to Sponsor and EC.
- 2. Possibly related to intervention/participation? This will require discussion and a decision Whether to report to Sponsor.
- 3. Not related to intervention/participation? This will need to be stored in the SAE spreadsheet.

All reported SAEs require full reporting and follow-up. This may require obtaining further information from the participant, facilitator of the DVPP or the women's worker.

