## 4 TRIAL DESIGN

This will be a pragmatic, parallel group individually randomised controlled pilot trial. We will be testing the feasibility and acceptability of the domestic violence perpetrator programme as well as the trial.

The domestic violence perpetrator programme (DVPP) will consist of a 26-week programme incorporating 22 weekly group sessions and 4 individual sessions. The sessions will be run by two experienced DVPP facilitators (one male and one female in order to model good gender role behaviours). The programme will start as a rolling programme, allowing new intakes of participants to join at specified intervals but after six months will become a closed programme, meaning that no new men will be able to join. This is to ensure that men will have completed the programme before the end of the pilot trial and to allow sufficient time for post-completion follow-up.

The weekly group sessions will incorporate most of the elements which exist in standard DVPPs. These include: goal identification and goal setting; recognising abuse; denial and minimisation; intents of violence; basic anger management; identifying urges to perpetrate abuse and cooling-down strategies; basic CBT; effects of DVA on partners and children; participant's own childhood experiences; impacts on children; active listening; conflict resolution; masculinity; beliefs and expectations; sexual respect; attachment styles; building empathy; loving relationships; emotional abuse; accountability.

Two pre-group individual sessions will assess suitability for the programme, will assess risk, and enable a needs assessment, and will begin relationship-building.

The remaining individual sessions will be tailored for participants' needs following the initial and ongoing assessment. Possible individual interventions might include deconstructing specific incidents of abuse; accountability letters or planning discussions with partner or children; relaxation or emotional regulation work.

New participants will only be able to join the group programme in specific weeks in order to minimise disruption to men already on the programme and to ensure that new men do not join in particularly challenging weeks (such as 'sexual respect). If there is a gap of more than two weeks between assessment and the next planned intake week, individual sessions will be scheduled in order to help the participants feel engaged with the programme and to reduce drop-out between assessment and programme start.

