7.3.13 Police offender reports

#### 7.4 Trial and follow-up assessments

Questionnaire measures will be repeated at 3, 6 and up to 9 months following randomisation (depending on time left between participant starting the study and the end of the study) and we will continue to try to collect these data even if the participant decides to just discontinue the intervention, unless they explicitly withdraw from intervention and trial. Consent will be checked prior to each data collection time-point. A reminder contact will be sent out to all participants 2-3 weeks before the next data point is due. We will try to accommodate participants' preferences for contact method (e.g. phone call, text, email, mail). Participants who withdraw from the trial or do not reply to three requests for questionnaire completion by whatever method however, will be defined as 'lost to follow up'.

Through in depth interviews with male perpetrators and brief interviews with intervention nonattenders as well as regular weekly updates between the research team and the intervention facilitators we will gain an understanding of retention issues and develop retention strategies for use in the full trial.

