## ADVERSE EVENTS (AE)

Researcher should complete the relevant form and forward to the Programme Manager who will add to the AE spreadsheet.

All SAEs and AEs will be reviewed by the members of the PSC/DMEC.

Sponsor: [name] ([contact]) CI: [name] ([contact]) DMEC Chair: [name] ([contact]) Programme Manager: [name] ([contact])

Amendment No.	Protocol version no.	Date issued	Author(s) of changes	Details of changes made
1	1.2	19.7.2017	KM	Addition of travel expenses for low waged men
				New male participant recruitment flyer
				Randomisation ratio change from 1:1 to 2:1
				Addition of past abuse to inclusion criteria
				Information sheet for professionals
2	2.0		MM	

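### Adverse events come to light by different routes in the two arms, so AE/SAE counts by arm are at risk of differential ascertainment

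*Protocol*

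**What the plan says.** **Who reports.** For SAEs, Appendix 5 says: "All SAEs should be reported and the relevant form completed by the researcher/facilitator". For other adverse events the same appendix names the researcher alone: "Researcher should complete the relevant form and forward to the Programme Manager who will add to the AE spreadsheet". On follow-up, Section 8.2 says "All SAEs will be followed up where appropriate by the researcher, the intervention coordinator or" the women's worker.

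**Contact in the intervention arm.** Section 4 describes a "26-week programme incorporating 22 weekly group sessions and 4 individual sessions". Appendix 4 gives "Up to 26 weekly visits of a DVPP". Section 7.4 adds "regular weekly updates between the research team and the intervention facilitators"; the purpose stated there is to understand retention, but it is also a standing channel through which events can reach the researchers.

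**Contact in the control arm.** Appendix 4 reads: "Control men (questionnaires only) Control women, support signposted". Follow-up questionnaires at 3, 6 and up to 9 months go to both arms, by post or in person. Under Section 7.4, each is preceded by a reminder and a consent check.

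**Support for women.** Section 7, step 7b, gives intervention women a dedicated worker and control women a generic women's worker. Section 7.1 and Appendix 4 describe signposting for control women.

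**Use of the data.** Section 3.3 names the Impact toolkit, interviews and the collection of adverse events as the measures for secondary objective 5 (willingness and risks of female partners). Section 9 presents secondary outcome measures by arm. The DMEC reviews safety data and advises whether to continue, modify or stop.

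**The concern.** A facilitator can complete an SAE form, and facilitators exist only in the programme arm. An event there has an extra route into the safety record. In the control arm it must surface through a questionnaire, a reminder contact, a women's worker if there is one, or a spontaneous report.

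The control route is also fragile. A postal questionnaire guarantees no conversation with a researcher, and participants who do not answer three requests are classed as lost to follow-up. A control man who stops replying then has no scheduled contact left. An intervention man who ignores questionnaires but attends sessions is still seen.

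Section 8 itself expects a high risk of AEs and SAEs in this population. If capture is less complete in controls, a table by arm would show more events under the programme even at equal true rates, or would shrink a real reduction. Serious events in control couples could also go unrecorded, which matters for oversight whether or not the arms are compared.

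**Working it through.** **1. The plan's own figures.** Sessions: 22 group + 4 individual = 26, matching Appendix 4. Allocation (Section 3): 36 × 2/3 = 24 intervention and 36 × 1/3 = 12 control. Both reproduce.

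**2. Scheduled contacts per man after randomisation.**

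| Counting rule | Intervention | Control | Ratio |
|---|---|---|---|
| Sessions + 3 questionnaires | 26 + 3 = 29 | 3 | 9.7 |
| Adding one reminder per questionnaire | 29 + 3 = 32 | 3 + 3 = 6 | 5.3 |
| As above, without the 2 pre-group sessions | 32 − 2 = 30 | 6 | 5.0 |

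These are upper bounds, since attendance is up to 26. They count contacts, not enquiries about adverse events. They apply to men only: the protocol gives no contact frequency for women's support, so no such ratio can be formed for women.

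**3. What unequal detection does.** Let p be the true risk in both arms, and dI and dC the probabilities that an event is recorded in the intervention and control arms. The observed ratio is (p × dI)/(p × dC) = dI/dC. The protocol gives no event or detection rates, so every value below is an assumption.

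| dI | dC | Observed ratio at equal true risk |
|---|---|---|
| 0.90 | 0.80 | 1.125 |
| 0.90 | 0.50 | 1.80 |
| 0.90 | 0.40 | 2.25 |

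With p = 0.30 and detection of 0.90 against 0.50, the expected recorded cases are 24 × 0.30 × 0.90 = 6.5 of 24 (27%) and 12 × 0.30 × 0.50 = 1.8 of 12 (15%).

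**4. Masking.** A true risk ratio of 0.5 would appear as 0.5 × 0.90/0.50 = 0.9, so a halving of risk would look like almost no effect.

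**5. No recorded control events.** With p = 0.20, the chance that none of the 12 control men has a recorded event is (1 − 0.20 × 0.90)^12 = 0.09 at 90% detection and (1 − 0.20 × 0.50)^12 = 0.28 at 50%.

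**6. Sources that already cover both arms.** Table 1 and Section 7.5 collect use of health services and contact with criminal justice at 3, 6 and 9 months from all participants. Section 7.3.13 lists police offender reports with no restriction by arm. Section 8.1 makes inpatient hospitalisation an SAE. Neither Section 8.2 nor Appendix 5 tells anyone to read the returned forms or police reports for such events. On the visible text, a control man's admission can be entered for costing without an SAE form.

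**The case against.** The strongest reply is that no comparison of adverse events by arm is announced. Section 9 limits the analysis to descriptive statistics, Section 8.2 keeps the statistician blinded to allocation for AE/SAE reporting, Section 8.3 speaks of overall safety data, and relatedness is judged case by case. This largely stands: counts by arm follow only from reading Sections 3.2, 3.3 and 9 together, and the baseline and 9-month presentation in Section 9 suits questionnaire scores better than event counts. But blinding and pooled review do not change which events reach the record.

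A second reply is that harm to women is also measured by the Impact toolkit, on the same schedule in both arms. That stands, and it means AE forms are not the only evidence for objective 5. It does not make SAE capture even.

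Third, the safety SOP (Appendix 1) and the external reporting policy are not in the text at hand and may specify elicitation. That stands and limits confidence.

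A reader might also infer more than the protocol supports:

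- That intervention couples are seen weekly. Only the men attend sessions.
- That control couples are seen through three questionnaires alone. There are also reminder and consent contacts, police reports, interviews planned with 5 control men and 5 control women, and possibly a generic worker.
- That control events have nobody to follow them up. Section 8.2 names the researcher and the women's worker as well as the intervention coordinator.

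**Conclusion.** The point holds as a risk of differential ascertainment. The facilitator route exists in one arm only, and the visible text describes no event enquiry common to both arms and no link from data already collected to the SAE route.

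It would go too far to say that the safety data will be biased, or that a wrong decision on the full trial would follow. Detection rates are unknown, and the progression criteria in Section 7.8 rest on recruitment and follow-up only. Nor does the illustration support distortion in either direction: if detection is lower in controls, the observed ratio is pushed one way, towards more events under the programme. That can look like harm or hide a benefit.

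The apparent ratio of 2.25 to 1.1 at equal true risk rests wholly on assumed detection of 90% against 40% to 80%. The roughly 5 to 10 to 1 contact ratio shows the imbalance in opportunity for men and is an upper bound. This is a cheap improvement worth making, held with moderate confidence because the SOP is not shown.

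**What to change.** In Section 8.2 and Appendix 5 (or by explicit reference to the SOP, if it already does this):

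1. Ask the same AE/SAE questions of men and women in both arms at 3, 6 and 9 months, with the existing questionnaires.
2. Have the researcher check each returned resource-use form, and the police reports, for events that meet Section 8.1, and complete the AE/SAE form.
3. Add a source field to the form: scheduled questionnaire, facilitator, women's worker, police or other.
4. Base any tabulation by arm on the common scheduled sources, and list facilitator- or worker-reported events separately. All events still go through the existing reporting route.

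Separately, reconcile Section 7, step 7b, with Section 7.1 and Appendix 4 on what contact control women have with a women's worker, because this determines whether that reporting route exists in the control arm.

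The cost is a short block of questions, one extra field and a small reconciliation task on data already collected. The downside is slightly longer questionnaires.
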